We will send one participation e-mail during the intervention participant's 30-day access period. One e-mail will be sent to each participant on day 4 of their 30-day access period.

Here is the day 4 participation encouragement e-mail subject line: ***Patient Well-Being Research Project- 26 more days to keep visiting us during your access time 😊***

b) Email to encourage survey completion:

We will send four of these survey completion emails to participants in both condition groups. For each data collection time (T2; T3), we will send two survey battery reminder e-mails. At T2, immediately after the intervention group participant's 30-day access period, and after 30 days have passed since the T1 baseline for the wait-list control participant (i.e., day 31), we will send one survey battery reminder e-mail. Four days later, we will send another survey battery reminder e-mail to those participants who have still not completed T2 data collection.

Here is the T2 (day 31) initial survey battery reminder e-mail subject line: ***Patient Well-Being Research Project: Reminder 7 days to complete Survey Set #2.***

IRB Study Number: TBD

Title: Patient Well-Being Research Project 01-23-17 to IRB

Here is the T2 (day 34/day 4 of 7-day window) initial survey battery reminder e-mail subject line: ***Patient Well-Being Research Project: Reminder 3 days to complete Survey Set #2.***

On the first day of T3, which corresponds to 60-days post baseline, we will send one survey battery reminder e-mail that the 7-day window is open for participants to complete the third survey battery set. Four days later, we will send another survey battery reminder e-mail to those participants who have still not completed T3 data collection.

Here is the T3 (60-day post baseline) initial survey battery reminder e-mail subject line: ***Patient Well-Being Research Project: Reminder 7 days to complete Survey Set #3.***

Here is the T3 (60-day post baseline) (day 64/day 4 of 7-day window) initial survey battery reminder e-mail subject line: ***Patient Well-Being Research Project: Reminder 3 days to complete Survey Set #3.***

Battery Set of Surveys Content

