Participant e-mail change requests. A function that will allow a consented participant to change their preferred e-mail address to receive research project communications will be built into the Table of Contents section of both online program conditions. This is to account for the possibility that a consented participant may cease to be employed at the University and thus lose access to her/his valid UM e-mail account to retrieve electronic gift card codes for redemption. As stated in the informed consent form section labelled, “Compensation for Participation in the Study”, it will be the responsibility of the participant to change their preferred e-mail on their own; they do not need to contact the research team offline.

In the unlikely event that a participant may wish to unsubscribe from receiving any further e-mails from the research team, we will no longer send them e-mail that they do not initiate. This means that the participant will not be able to receive the electronic gift card codes for any incentives they may be owed. The following required statement and unsubscribe link is embedded in all e-mails the participant will receive from the research team:

IRB Study Number: TBD

Title: Patient Well-Being Research Project 01-23-17 to IRB

“To prevent future emails regarding Fun For Wellness, please go to the following link: [unsubscribe](#)”

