From the computer programming perspective, as soon as the participant confirms that he or she would like to unsubscribe and they submit their request, a backend database will continue to track their unique ID number linked research activities throughout the study and will maintain a log of every electronic gift card code they will be owed at the end of the study. If after unsubscribing and at the end of the 60-day study, the unsubscribed participant would like to obtain the incentives owed to them, they must go in person to the UM School of Education and Human Development to retrieve their incentives. The participant must present their unique ID number to the secretary at the UM School of Education and Human Development and request their owed electronic gift card codes. The secretary will go to a website built specifically for the purpose of retrieving electronic gift card codes for Patient Well-Being Research Project participants who officially unsubscribed from receiving e-mails. The secretary will enter the participants' unique ID number into the website fields and the website will print out a list of all the electronic codes owed to the participant. The secretary will hand the list of electronic gift card codes to the participant. The participant will then be able to enter the codes at the Amazon website to redeem the electronic gift cards.

From the participant's perspective, When they click the unsubscribe link, it will not immediately unsubscribe them. It will first present them with a pop-up message description of the effects of unsubscribing and a button to allow them to unsubscribe if that is their choice (see message below of description of effects of unsubscribing). The description will explain that by unsubscribing they will no longer be able to receive their Amazon electronic gift code(s) via e-mail. The unsubscribe description will inform them that if they truly wish to unsubscribe given the effects of this action (i.e. loss of Amazon gift card code access via e-mail), they will have the

IRB Study Number: TBD

Title: Patient Well-Being Research Project 01-23-17 to IRB

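### A confirmed unsubscribe ends all remaining T2/T3 survey e-mails for participants who have not withdrawn; the pop-ups mention only gift codes, and the intervention arm gets one more such link before T2

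*Combined protocol and SAP*

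**What the plan says.** **Unsubscribing** (Participant e-mail change requests, and the pop-up texts after it).

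- The "unsubscribe link is embedded in all e-mails the participant will receive from the research team". Its label reads: "To prevent future emails regarding Fun For Wellness, please go to the following link".
- A click is not enough: "When they click the unsubscribe link, it will not immediately unsubscribe them". Pop-up #1 follows, with a button to confirm and a button to cancel.
- After confirmation, "we will no longer send them e-mail that they do not initiate".
- The effect the participant is told about is that "by unsubscribing they will no longer be able to receive their Amazon electronic gift code(s) via" e-mail. Pop-ups #1 and #2 then give instructions for collecting the codes in person. Neither mentions surveys.
- The person stays in the study: "a backend database will continue to track their unique ID number linked research activities throughout the study", and the incentives owed are still logged.

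**Survey prompts** (Remuneration Plan; items 9 and 10 of the recruitment window procedures). T2 and T3 prompts are described only as e-mails: "We will send four of these survey completion emails to participants in both condition groups". The Data Collection Plan treats a survey not completed within its 7-day window as missing.

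**Other e-mails after randomization.** Item 9 sends a welcome e-mail to everyone randomized. Item 10(a), which concerns the intervention participant's access period, adds: "One e-mail will be sent to each participant on day 4 of their 30-day access period".

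**The concern.** The link is described by what it does to program e-mail, but it ends all contact that the team initiates. The survey e-mails carry the project's name in their subject lines, not the Fun For Wellness name in the footer. A participant tired of program e-mail has no reason to expect the survey invitations to stop too, and the confirmation screens do not say so. Item 5 (Informed Consenting) gives the contact address two uses, data collection reminders and gift codes. The pop-ups disclose the loss of only one.

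Outcome data may therefore be lost from people who never chose to leave. Those put off by the program are plausible unsubscribers, and their answers matter for effectiveness and for acceptability, which is a stated objective. The FFW Experience Survey is given once, at T2, to the intervention arm only, so it is exposed to the same loss. The Data Analysis Plan names no method for missing outcomes and no comparison of attrition by arm. Attrition rates appear there only as inputs to power simulations.

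**Working it through.** **1. The plan's own count.** Two survey time points (T2, T3) with two e-mails each give 2 × 2 = 4, which matches item 10(b). The second e-mail of each pair goes only to those who have not yet completed.

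**2. What a confirmed unsubscribe removes.** This depends on when it happens:

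- from the welcome or day-4 e-mail: all 4 survey e-mails;
- from the first T2 e-mail: at most the remaining 3;
- from the first T3 e-mail: at most 1.

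**3. Links by arm, after randomization and before the first T2 e-mail.**

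- Intervention: welcome + day 4 = 2.
- Control: welcome = 1.

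The account-verification e-mail and the T1 reminder come before randomization and cannot differ by arm.

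**4. Size, by illustration.** The documents give no unsubscribe rate. Assume that each e-mail carries the same chance u of a confirmed unsubscribe in both arms. Enrollment at the maximum of 500 with 2:1 allocation gives about 333 and 167. Then:

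- intervention: P(cut off before T2) = 1 − (1 − u)²
- control: P(cut off before T2) = u
- difference = u − u² = u(1 − u)

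| Assumed u | Intervention | Control | Difference (points) | People (of 333 vs 167) |
|---|---|---|---|---|
| 0.5% | 1.0% | 0.5% | 0.5 | 3.3 vs 0.8 |
| 1% | 1.99% | 1.0% | 0.99 | 6.6 vs 1.7 |
| 2% | 3.96% | 2.0% | 1.96 | 13.2 vs 3.3 |
| 5% | 9.75% | 5.0% | 4.75 | 32.5 vs 8.3 |

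Example at 5%: 1 − 0.95² = 0.0975, and 0.0975 × 333 ≈ 32.5.

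**5. What the illustration does not show.** Because u is the same in both arms, the model contains no effect of disliking the program. The arm difference comes entirely from the one extra e-mail. The welcome e-mail, sent to both arms, produces about half of the intervention-arm cut-offs and all of those in control. The table shows how many people would lose their prompts. It does not show how many would miss the survey or how far the treatment comparison would shift.

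**The case against.** The strongest reply is that this is a rare event with a real safeguard. The protocol calls unsubscribing unlikely. A confirming click is required, and it comes just after a warning that gift codes must then be fetched in person, which is a deterrent. Ending all unsolicited e-mail for someone who asks for that is also a legitimate choice. All of this stands, and it favours the low end of the table. It does not remove the problem, because the confirmation screen is where the survey consequence is left out.

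A reader might draw four stronger conclusions that the documents do not support:

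- *A click on the footer stops the surveys.* It does not. Cancelling at pop-up #1 leaves all study e-mail in place.
- *An unsubscribed participant is lost to follow-up.* Surveys are completed on the website, both arms may still log in after day 30, and nothing closes an unsubscribed account. What is lost is the prompt. Missing data is likely, not automatic.
- *Participants are never told.* Pop-up #2 does confirm that the e-mail account has been unsubscribed. The consent form is not available here and may describe the survey schedule or how to withdraw. The gap can be shown only for the footer and the two pop-ups.
- *The T2 and T3 comparison is biased.* One extra link in one arm makes differential loss possible. Nothing in the documents shows that it would occur or that it would be related to outcome.

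**Conclusion.** The point holds in a limited form. A confirmed unsubscribe cuts the remaining survey contact with someone who is still in the trial. The screens at which it is confirmed do not say so, no other survey prompt is described, and a missed window counts as missing. For those affected, avoidable loss of outcome data is likely.

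The imbalance in exposure is exactly one link before T2 (two versus one). Over an assumed 0.5% to 5% per e-mail, the gap between arms in people cut off before T2 is about 0.5 to 4.8 percentage points. This rests on an equal rate per e-mail in both arms, full enrollment and 2:1 allocation. The true rate is unknown, and any bias may be small. The case for change rests on the low cost of the remedy and on participants knowing what they are switching off, not on a demonstrated distortion of the result.

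**What to change.** - **Pop-up #1:** offer two choices: (a) stop program encouragement e-mails and keep survey invitations; (b) stop all study e-mail.
- **For choice (b):** state in both pop-ups that survey invitations will stop. Show the participant's own T2 and T3 opening and closing dates with the log-in link. Offer leaving the study as a separate, recorded choice.
- **Reporting:** count unsubscribed-but-not-withdrawn participants by arm in the participant flow, so that the unknown rate becomes visible.
- **Footer:** the protocol describes this statement as required without giving the source. Keep it unless that source allows rewording; the changes above do not depend on it.

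The cost is revised pop-up text, one preference flag in the mailing program, and IRB approval of the wording. The downside is one extra click for someone who wants no e-mail at all.

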Appendix

BET I CAN Studies

Drivers of Change	Skill	Study	Description	Key Outcomes
Behaviors	Set a goal	Coote & MacLeod (2012)	
 • Effect of brief, self-help positive goal-focused intervention—Goal-setting and Planning (GAP) Skills training—on well-being in people with depression • Randomization (GAP or wait-list control) 
 • Groups assessed pre-intervention, post-intervention, and 5-weeks after completing intervention 	
 • Compared to wait-list control group, intervention group showed significant improvements overall (decrease in negative affect, depressive symptoms; increase in positive affect and life satisfaction) post-intervention and at 5-week follow up.
Behaviors	Set a goal	Morisano et al (2010)	
 • Effect of online goal-setting program (one session) for college students with academic difficulty on academic achievement • Eight step goal-setting “package” designed to involve number of factors related to effective goal pursuit; Eight steps: 
 • (1) Contemplate desired future; (2) Identify goals; (3) Prioritize goals; (4) Explore positive goal outcome expectations; (5) Determine subgoals; (6) Identify potential obstacles and strategies for overcoming; (7) Set benchmarks for goal attainment; (8) Evaluate goal commitment 	
 • After four months, goal-setting group had significant improvements in academic performance compared with the control group. • Specificity of goal (number of words used to describe ideal future) was significantly related to greater academic improvements.

			
 • Randomized, controlled intervention with two groups: goal-setting group and control group 	
Behaviors	Set a goal	Wilson & Brookfield (2009)	
 • Effect of goal setting on motivation and adherence in a six-week exercise program • Random assignment (3 groups: process goal, outcome goal, no goal) 
 • Process goals focus on the processes to engage in (e.g., maintain certain heart rate for 30 minutes of 40 minute exercise session) • Outcome goals focus on the end point (e.g., lose 5 pounds) • Motivation measured at baseline and at end of program (6weeks); Adherence measured throughout, 3 months post and 6 months post 	
 • Motivation and adherence significantly greater for process goal group compared to outcome goal and no goal groups. • During intervention, process goal and outcome goal had greater adherence than no goal group. Post-intervention (3 and 6 months), process goal group had greater adherence than outcome and no control groups.
Behaviors	Create positive habits	Adriaanse et al (2011)	
 • Three experiments examined the cognitive effects of implementation intentions specifying replacement of habitual response with alternative response on breaking habits • Implementation intentions specify an intention and can be used to link a new desired behavior to a situation that triggers a habitual behavior (e.g., If I am in situation X, then I will perform goal-directed behavior Y) 	
 • Implementation intentions eliminated the advantage of habitual response in a triggering situation.
Behaviors	Create positive habits	Chipperfield et al (2008)	
 • Efficacy of habit-based intervention on weight for overweight adults 	
 • Intervention condition lost significantly more weight over 8 weeks than the control condition.

			
 • Randomized to intervention or wait-list control condition • Intervention group received leaflet on habit formation and simple recommendations for eating and activity behaviors • Assessed weight change over 8 weeks for intervention condition compared with control condition and over 32 weeks in the intervention condition 	
At 32 weeks, those from the intervention condition who remained in the study showed a pattern of continuing weight loss.

Behaviors	Create positive habits	Turk et al (2013)	
 • Effect of feedback frequency and self-monitoring daily food intake and physical activity on weight loss over 24-months • Randomly assigned to one of three self-monitoring methods with either no daily feedback messages or daily feedback messages (paper diary, no feedback; digital diary, no feedback; digital diary, daily feedback) • All participants received feedback about eating and physical activity on weekly basis for first four months and bi-weekly for the next two months • Daily feedback message based on individual's recorded information (e.g., try a little harder to watch high calorie, high fat foods; nice food choices, this will serve you well) 	
 • Receiving daily feedback messages significantly increased self-monitoring adherence. • Self-monitoring adherence was significantly associated with weight loss. • Feedback frequency significantly related to weight loss but after adjusting for self-monitoring adherence this effect was no longer significant.
Emotions	Collect positive emotions	Emmons & McCullough (2003)	
 • Three studies examining the effect of gratitude on psychological and physical well-being 	
 • Daily gratitude thoughts led to increase in positive emotions, but only weekly gratitude thoughts

			
 In first two studies, participants randomly assigned to 1 of 3 conditions (hassles, gratitude listing, and either neutral life events or social comparison) and kept weekly or daily records; In third study, clinical sample was randomly assigned to gratitude condition or to a control condition 	
over longer periods of time led to longer-term states of (physical) well-being.
 
 In the clinical sample (study 3), daily gratitude notes also resulted in a decrease in negative emotions.
Emotions	Collect positive emotions	Gander et al (2013)	
 Effect of nine strength-based positive interventions on well-being and depression Online randomized placebo-controlled study (9 intervention groups and one placebo control group); degree of happiness and depression measured at five times (pre- and post-test, 1-, 3-, and 6 month follow-up) 	
 Eight of nine interventions increased happiness; depression decreased in all groups.
Emotions	Collect positive emotions	Ouweneel et al (2014)	
 Effect of two positive psychological interventions (focused on thoughts of gratitude or acts of kindness) on enhancing study-related positive emotions and academic engagement for college students Two randomized controlled trials with experimental (thoughts of gratitude or acts of kindness) and control conditions Gratitude condition: prompted to think of people they are grateful for each day in a different domain; Kindness condition: given instructions each week to focus on five acts of kindness per day and report on them in the evening 	
 Gratitude intervention had significant positive effect on positive emotions. Kindness intervention had positive influence on positive emotions and academic engagement.

			
 Monitored on a daily basis during the one-week intervention, and additional pre-, post-, and follow-up assessments 	
Emotions	Cope with negative emotions	Kemeny et al (2012)	
 Effect of an 8-week meditation/emotion regulation training intervention on negative emotions and prosocial responses Randomly assigned to training group or wait-list control group; assessed changes in emotional behavior pre, post, and 5 months after training completion 	
 The training group reported reduced trait negative affect, rumination, depression, and anxiety, and increased trait positive affect and mindfulness compared to the control group. Most effects maintained at follow-up.
Emotions	Cope with negative emotions	Robins et al (2012)	
 Effects of mindfulness-based stress reduction intervention on emotion experience and expression Randomized to intervention or wait-list control group 	
 Compared with WL, intervention completers reported significantly greater increases in trait mindfulness and decreases in absentmindedness, greater increases in self-compassion, and decreases in fear of emotions, suppression of anger, aggressive anger expression, worry, and difficulties regulating emotions.
Emotions	Cope with negative emotions	Yu-Hsin Liao et al (2012)	
 Effects of experiential self-focus writing on negative affect after an interpersonal hurt College students who had experienced interpersonal hurt were randomly assigned to experiential self-focus condition (write about feelings and experiences related to the hurt) or to control writing condition (write about neutral event) 	
 Negative affect resulting from an interpersonal hurt significantly decreased over time among participants in the experiential self-focus writing group compared with the control group.

Thoughts	Challenge assumptions	Hofmann et al (2009)	
 • Effect of reappraisal, acceptance, and suppression strategies on anxious arousal • Randomly assigned to one of three different emotion regulation strategies (Reappraisal, Suppression, or Acceptance) and asked to give an impromptu speech • The Reappraisal group was instructed to regulate their anxious arousal by reappraising the situation; the Suppression group was asked to suppress their anxious behaviors; and the Acceptance group was instructed to accept their anxiety 	
 • Overall, reappraisal was most effective strategy for regulating anxious arousal. • Both reappraising and accepting anxiety was more effective for moderating the physiological arousal than suppressing anxiety. • Reappraising was more effective for moderating the subjective feeling of anxiety than attempts to suppress or accept it.
Thoughts	Challenge assumptions	Rodebaugh et al (2009)	
 • Undergraduate students high in social interaction anxiety divided into high purposeful engagers (tend to purposefully engage with unpleasant thoughts and be open to different perspectives) and low purposeful engagers (tend not to actively engage with unpleasant thoughts or consider alternative views) • Randomly assigned to 25-min unstructured writing condition about social situation or to 25-min structured writing condition with cognitive restructuring prompts 	
 • Low purposeful engagers who did not receive cognitive restructuring prompts reported worsened mood at the end of the study, whereas low purposeful engagers who received the prompts and high purposeful engagers in both conditions did not report as much deterioration in mood.
Thoughts	Challenge assumptions	Shurick et al (2012)	
 • Effect of cognitive restructuring (CR) on conditioned fear responses and whether this effect persists over time (24 hr) 	
 • Compared with control participants, CR participants demonstrated a reduction in fear and EDA across sessions.

			
 • Cognitive restructuring is individually tailored to help individuals better understand their own experience of anxiety and reinterpret stimuli in a less negative way • Conditioned participants using images of snakes or spiders that were occasionally paired with a mild shock to the wrist—obtained subjective fear reports and electrodermal activity (EDA) • Randomly assigned after conditioning to either CR training group (aimed at decreasing emotional response to the shock and the conditioned stimuli) or control group • All participants returned 24 hr later to repeat the conditioning session 	
Thoughts	Write a new story	Good et al (2003)	
 • Effect of an intervention to reduce the effects of stereotype threat on adolescents' standardized test performance • Students in the experimental conditions were mentored by college students who encouraged them either to view intelligence as malleable or to attribute academic difficulties to the novelty of the educational setting; Control group: mentored by college students and taught about the dangers of drug use 	
 • Results showed that females in both experimental conditions earned significantly higher math standardized test scores than females in the control condition. • Students (male and female) in experimental conditions earned significantly higher reading standardized test scores than participants in control condition. • Encouraging students to make nonpejorative attributions for

			
 Participants in study were from a rural school district serving a largely low-income Hispanic population (students who face negative stereotypes about their abilities) 	
their difficulties was associated with an increase in achievement.

Thoughts	Write a new story	Korte et al (2012)	
 Effect of life review therapy for older adults with moderate depressive symptomatology Randomly assigned to either life review therapy or care as usual; Assessed depressive symptoms and secondary outcome measures at baseline, post-intervention (3 months after baseline), follow-up (3 months after end of intervention) and intervention group assessed again at 9 months post intervention The intervention has three core elements. First, the integration of difficult life events from the past; second, the development of agentic life stories, which helps the participants to cope with present life events and to formulate new goals; third, the retrieval of specific positive memories, which can serve as building blocks of the new life stories 	
 Life review therapy was effective in reducing depressive symptoms and these effects were maintained at follow-up. It also had a positive effect on well-being.
Thoughts	Write a new story	Schroder et al (2014)	
 Effect of mindset induction on cognitive control brain activity Randomly assigned to either growth-mindset condition or fixed-mindset condition and then completed reaction-time task 	
 Inducing a growth mindset resulted in enhanced attention to task-relevant stimuli, whereas inducing a fixed mindset enhanced attention to responses.

			
 • Growth-mindset: malleability of intelligence • Fixed-mindset: immutability of intelligence 	
 • Despite enhanced attention to responses in the fixed-mindset group, this attention allocation was unrelated to adaptive performance adjustments. In contrast, enhanced attention to errors in the growth-mindset group was related to adaptive performance. • Attention allocation to errors was directly associated with post-error improvement in the growth condition only. •
Interactions	Connect	Bond et al (2003)	
 • The role of changes in Alcoholics Anonymous (AA) involvement and social networks in relation to abstinence following substance abuse treatment • Individuals seeking treatment were interviewed at intake and re-interviewed 1 and 3 years later to collect information about alcohol consumption, dependence symptoms, social support for reducing drinking, number of heavy drinkers in the social network and AA involvement 	
 • Significant predictors of 90-day abstinence at both the 1- and 3-year follow-up interviews included AA involvement in the last year, percentage of heavy or problem drinkers in the social network, percentage encouraging alcohol reduction and AA-based support for reducing drinking.

				
 AA involvement and the type of support (alcohol-specific) received from AA members were consistent contributors to abstinence 3 years following a treatment episode. AA-based contacts supporting reduced drinking were more significant contributors to long-term abstinence than non-AA based contacts supporting reduced drinking.
Interactions	Connect	Bradley & Gottman (2012)	
 Effect of a skill-based couple and relationship education program for low-income, situationally violent couples with children Skills include: functional vs. dysfunctional communication patterns, strengthening communication skills, conflict management, information and skills related to intimate relations/sexual intimacy 
 Relationship skills were measured at three time points (baseline, post-intervention and long-term post-intervention) using the Reduced Sound Relationship House Questionnaire (Gottman, 1994, 1999) which is divided into four domains related to relationship skills (friendship, sex/romance/passion, shared 	
 Violence was reduced via an increase in intervention-based relationship skills.

			
meaning, and conflict management); Scores from the four domains were summed to create a “healthy relationship skills” score for each time point
 
 • Couples randomly assigned to a treatment or no-treatment control group; self-reported attitudes reflecting healthy relationship skills and intimate partner violence at multiple time points 	
Interactions	Connect	Gable et al (2006)	
 • Examine experience of sharing successes (talking about a recent positive event in his or her life; e.g., receiving a good grade or being offered a job) with romantic partner • Dating couples participated in videotaped interactions in which they took turns discussing recent positive and negative events • Couples completed self-report measures of relationship well-being; each partner rated how understood, validated, and cared for they felt in each discussion; outside observers coded responders’ behavior (ratings of active-constructive behavior) 
 • Active and constructive responses communicate positive information about the event itself and convey positive information about the personal significance of the event for the individual 	
 • Both self-report data and observational codes showed that 2 months later, active and constructive responses to positive event discussions were more closely related to relationship well-being and break-up than were responses to negative event discussions.

Interactions	Communicate	Bodie et al (2015)	
 • Effect of active listening on perceptions of listener helpfulness, sensitivity, and supportiveness and discloser emotional improvement • Undergraduate students randomly assigned to disclose a recent upsetting problem to either a trained active listener or an untrained listener 
 • Active listeners: trained to ask open questions, paraphrase content, reflect feelings, use assumption checking and are nonverbally immediate • Nonverbally immediate behaviors include head nods, eye contact and forward body lean 	
 • Both verbal and nonverbal active listening behaviors were rated as signaling more emotional awareness and promoting a greater degree of emotional improvement.
Interactions	Communicate	Lin et al (2004)	
 • Effect of an assertiveness training program on nursing and medical students' assertiveness, self-esteem, and interpersonal communication satisfaction • Assertiveness training focused on several skills: proper assertive behavior, clarification and confirmation of the individual's fundamental rights, confronting criticism, expressing dissatisfaction, refusals, and requests, and communication skills • Longitudinal research design with participants with low assertiveness; assigned to experimental group or comparison group 	
 • The assertiveness and self-esteem of the experimental group were significantly improved in nursing and medical students after assertiveness training.

Interactions	Communicate	Weger et al (2014)	
 • Effect of active listening in initial interactions on feeling understood • Participants engaged in interactions with confederates trained to respond with active listening messages, advice, or simple acknowledgements 	
 • Participants felt more understood when they received an active listening response.
Context	Read the cues	Carpenter et al (2014)	
 • Effects of both level of smoking involvement (daily vs. occasional smoking) and gender on reactivity to both smoking and alcohol cues • Cue-reactivity paradigm is well suited to examine one marker of dependence: craving related stimulus control (i.e., the ability of environmental cues to elicit craving to smoke) • Smokers (daily and occasional) were exposed to each of three counterbalanced cues: 
 • In vivo smoking (sight, smell, lighting of cigarette) • Alcohol (opening, pouring, and smell of preferred beverage) • Neutral cue 	
 • Daily smokers exhibited higher levels of non cue-elicited craving than did occasional smokers. • Both daily and occasional smokers showed significant increases in craving in response to cues (i.e., cue-elicited craving), with little evidence that cue-elicited craving differed between groups. • Females were more cue reactive to both the alcohol and smoking cues than males.
Context	Read the cues	Martins & Vallen (2014)	
 • Two studies examined the presence vs. absence of holiday food cues on consumption of snack food for dieters vs. non-dieters • Study 1 (quasi-experimental design) evaluated snack-food consumption on a holiday vs. a non-holiday • In Study 2 (true experimental design), participants read primes associated with 	
 • In study 1, dieters consumed more of a food item on an ordinary day relative to a holiday; the consumption patterns of non-dieters did not vary based on holiday cues. • Study 2 demonstrated that dieters, but not

			
holiday eating, holiday history, or a neutral topic. The bolstering of self-regulatory resources when facing holiday related cues was explored
	
non-dieters, bolster self-regulatory resources to a greater extent in the presence vs. absence of a holiday food cue.

Context	Read the cues	Prinsen et al (2013)	
 Examines the role of environmental cues in steering people’s dietary decisions in response to food temptations Conformity to environmental cues about food intake was assessed in a local bakery (study 1) and a lab setting (study 2); participants were unobtrusively presented with a bowl of individually wrapped chocolates. The presence of empty wrappers was manipulated, to indicate whether others who had been in the same situation had or had not eaten the chocolates Study 3 assessed conformity to environmental cues about food choice; participants were required to choose between a healthy and an unhealthy snack (food wrappers indicated whether previous participants had chosen the healthy or the unhealthy snack) 	
 Participants were more likely to take chocolates in the presence of an environmental cue that others did too. Participants were more likely to choose a snack that was consistent with the choice of others.
Context	Read the cues	Wansink & Payne (2007)	
 Effect of environmental cues on food intake Examine if people would eat less if they knew how much they had already eaten Tables randomly assigned to be bussed (leftover wings removed) or unbussed (wings left on table) 	
 People at the unbussed tables ate significantly less than people at the bussed tables.

Context	Change the cues	Janse Van Rensburg et al (2013)	
 • Effect of light and vigorous intensity aerobic exercise on cigarette cravings, subjective and physiological reactivity to smoking cues, and affect after overnight nicotine deprivation • Smokers (deprived of nicotine overnight) randomized to one of three exercise conditions (light intensity, vigorous intensity, or a passive control condition) • After each exercise condition, participants engaged in a standardized cue reactivity assessment • Self-reported urges to smoke, affect, and salivary cortisol were assessed at baseline (i.e., before each condition), immediately after each condition, and after the cue reactivity assessment 	
 • Light and vigorous exercise significantly decreased urges to smoke and increased positive affect, relative to the passive control condition.
Context	Change the cues	Lai & Good (2005)	
 • Effect of soft music on sleep quality for older adults • A randomized controlled trial (control group and music group) was used with a two-group repeated measures design • Participants listened to their choice among six 45-minute sedative music tapes at bedtime for three weeks 	
 • Music resulted in significantly better sleep quality in the experimental group.
Context	Change the cues	Papies & Hamstra (2010)	
 • Effect of attractive food cues on eating behavior for dieters and non-dieters • Effect of activating the dieting goal before participants entered the tempting eating situation on self-regulation 	
 • Dieters ate more than non-dieters in the no priming condition. However, dieters reduced their eating behavior when primed with dieting goal, whereas this

			
 Assessed the number of snacks consumed (after primed with dieting goal or not) in a local store where the smell of grilled chicken was present 	manipulation did not affect consumption for non-dieters.
